**BACKGROUND/PURPOSE:**

EUS is well established as a diagnostic tool in the adult population, introduced clinically in the 1980s,[1] but its uses in pediatrics are still emerging. In children EUS is primarily used as a diagnostic tool for evaluation of pancreaticobiliary disease.[2-6]

Pancreatitis has been increasing in incidence in both adult and pediatric populations, requiring providers to increasingly recognize, accurately diagnose and care for patients with ARP and CP[7, 8]

To maximize the success of interventions aimed at slowing or stopping disease progression and ameliorating the deleterious downstream effects of pancreatic insufficiency, techniques capable of identifying the early stages of chronic pancreatic disease are urgently needed.

The advantage of EUS over other diagnostic techniques is the high detail characterization of parenchymal and duct findings of pancreatitis. While adult Rosemont or conventional criteria are in use for EUS diagnosis of CP in adults, validated pediatric criteria do not exist.[9-12] The Rosemont and conventional criteria are nonetheless used for pediatric patients, as there are no reasonable alternatives. To date, EUS findings of CP in children have not been systematically studied.

In addition to grayscale characterization, ultrasound provides the opportunity to quantify tissue stiffness as a biomarker of fibrosis using elastography. Shear wave elastography (SWE) provides operator independent, true quantitation of tissue stiffness and is available on both EUS and transabdominal ultrasound (TUS) systems. Both TUS and EUS SWE have been studied for diagnosis of CP in adult patients,[13-17] however they have not been studied in pediatric pancreatitis.

The Pancreas Care Center at Cincinnati Children's Hospital Medical Center (CCHMC) and the large population it serves places us in a unique position to study EUS and ultrasound elastography in pediatric patients and address these gaps in the literature.

**SPECIFIC AIMS**

The aims of the proposed study are as follows:

**Aim 1: Characterize endoscopic ultrasound (EUS) findings of pediatric acute recurrent pancreatitis (ARP) and chronic pancreatitis (CP).**

Adult criteria for EUS diagnosis of CP exist, but no such criteria exist for children. As such, the applicability of current diagnostic criteria to pediatric patients is unknown.

**1.1: Catalogue grayscale EUS findings of ARP and CP in a pediatric cohort and compare to healthy controls. Hypothesis:** EUS findings of ARP and CP in pediatric patients will differ from those of adult ARP and CP and will be characteristically different

from healthy controls. *Exp1:* We will catalogue grayscale EUS findings in 40 pediatric patients with known history of ARP or CP undergoing clinically indicated EUS and will compare those with findings in 20 patients without a history of pancreatitis who are undergoing EUS for other indications.

**1.2: Benchmark grayscale EUS against other imaging modalities for diagnosis of CP, particularly early CP, in children.** *Hypothesis:* Grayscale EUS findings will be more sensitive than other imaging modalities in all stages of CP. *Exp2:* We will test associations, in blinded fashion, of grayscale EUS findings catalogued under S.A1.1 in enrolled children with findings on alternative pancreas imaging modalities performed for clinical indications. Specifically, we will correlate to endoscopic retrograde cholangiopancreatography (ERCP), magnetic resonance cholangiopancreatography (MRCP) and computed tomography (CT) performed for clinical indications within +/- 3 months of the EUS.

**Aim 2: Define the diagnostic performance of ultrasound elastography for CP and pancreatic stiffness as a measure of fibrosis in pediatric patients.**

**2.1: Define the diagnostic performance of EUS and TUS elastography for pediatric CP.** *Hypothesis:* EUS and TUS elastography will have high specificity for CP with increased stiffness in patients compared to controls. *Exp 1:* Patients enrolled under Aim 1 will undergo shear wave elastography (SWE) measurement of the pancreas during EUS. These same patients will undergo research TUS with SWE of the pancreas. SWE results by both EUS and TUS will be evaluated for diagnostic performance for CP.

**2.2: Define agreement between EUS and TUS measurement of pancreatic parenchymal stiffness in pediatric patients.** *Hypothesis:* EUS and TUS measures of pancreatic parenchymal stiffness will agree with minimal bias. *Exp2:* EUS and TUS SWE data obtained under S.A2.1 will be evaluated for agreement and divergent cases will be investigated to define causes.

**2.3: Define the diagnostic performance of elastography for pancreatic fibrosis.** *Hypothesis:* SWE is a sensitive indicator of pancreatic fibrosis as identified by histology. *Exp3:* Patients undergoing clinically indicated total pancreatectomy and islet auto transplant (TPIAT) or other pancreatic surgical resection at our institution (approximately 20 per year) will be approached to undergo pre-operative TUS SWE. These SWE measurements, along with EUS SWE measurements obtained preoperatively, will be compared to binary and semi-quantitative assessments of pancreatic parenchymal fibrosis by histology.

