### **STUDY PROCEDURES:**

Approximately 60 participants will be recruited to enroll in the study. Forty participants will have ARP or CP as defined by the International Study Group of Pediatric Pancreatitis: In search for a cure (INSPIRE)[18]. Twenty participants from this cohort will be undergoing TPIAT or other pancreatic resection. Another twenty participants will be controls with no history of pancreatic disease undergoing EUS for other clinical indications.

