#### *Procedures and Imaging:*

EUS will be performed as part of routine clinical care using a GF-UCT180 curvilinear array ultrasound gastroscope (Olympus America Inc; Center Valley, PA). Grayscale findings (Table 1) will be recorded and documented for clinical care. Research EUS SWE measurements will be obtained using the Aloka Arietta 850 AT processor (Olympus America Inc; Center Valley, PA) with SWE measurements taken from each of the head, genu, body and tail of the pancreas. Research TUS SWE will be performed using a Canon Aplio i800 ultrasound system and a curved 1-6 MHz transducer. 2D SWE will be performed with measurement of shear wave speed in the head, body and tail of the pancreas.

Modality	Findings
EUS	Rosemont and Conventional Criteria
MRI	Atrophy T1 signal (signal intensity ratio, relaxometry) Enhancement Cambridge Criteria
CT	Atrophy Calcifications Duct dilation
ERCP	Cambridge Criteria

**Table 1:** EUS and other imaging findings to be catalogued and compared for diagnosis of CP

MRCP or CT imaging within 3 months of the EUS will be reviewed blinded to EUS and SWE findings for findings of CP (Table 1). Fluoroscopic pancreatogram images from patients with an ERCP within this time frame will be scored using Cambridge Criteria.[19]

Research EUS SWE measurements are anticipated to add approximately 5 minutes to the total procedure time. Research TUS SWE will take no more than 20 minutes and may or may not occur on the same day as the EUS procedure.

**Specimen histology:** A small core of pancreatic tissue is routinely collected from all patients undergoing TPIAT at our institution and a similar sample would be obtained from patients undergoing other resections. Findings from enrolled participants' samples will be reviewed for the presence of fibrosis using a four-stage scoring system adopted by Wellner et al.

Data collected from Epic may include: patient age, sex, height/ weight, relevant lab values, results of imaging modalities (MRCP, CT, US, or ERCP, EUS), relevant genetic testing results, pancreatic function testing results, medications, hospital stay, complications, clinical course, interventions/surgical procedures, and other relevant clinical data.

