#### **Statistical analysis:**

*Power calculation:* Given that this is a pilot and feasibility study, a power calculation was not performed. We plan to approach for enrollment all pediatric patients that meet inclusion criteria during the funding period and anticipate no difficulty achieving our recruitment targets based on the robust referral base for our pediatric Pancreas Care Center.

*Aim1:* Frequencies will be used to describe the presence of EUS findings in patients with ARP, CP and controls. Groups will be compared using Fisher's exact and Chi-square tests as appropriate. These tests will also be used, as appropriate to compare the relationship between EUS and other imaging findings.

*Aim2:* Means, standard deviations, 95% confidence intervals will be used to describe TUS and EUS SWE results for patients with ARP, CP and for controls. Agreement between TUS and EUS SWE will be analyzed using Pearson correlations, intraclass correlation coefficients and Bland-Altman analyses. Sensitivity and specificity and 95% confidence intervals will be calculated for diagnosis of CP by SWE using INSPIRE criteria and for prediction of the presence of fibrosis on histology.

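### Aim 1.2 benchmarks grayscale EUS for diagnosing CP on a sensitivity hypothesis, but no accuracy measure, and no specificity in particular, is planned for EUS or its comparators

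*Combined protocol and SAP*

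**What the plan says.** The title of Aim 1.2 (Specific Aims) is "Benchmark grayscale EUS against other imaging modalities for diagnosis of CP, particularly early CP, in children". The hypothesis beneath it is "Grayscale EUS findings will be more sensitive than other imaging modalities in all stages of CP". The experiment is described as testing associations and correlating EUS findings with ERCP, MRCP and CT "performed for clinical indications within +/- 3 months of the EUS".

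For Aim 1, the Statistical analysis section plans frequencies of EUS findings in ARP, CP and controls, compared by Fisher's exact and Chi-square tests. On other imaging it adds only: "These tests will also be used, as appropriate to compare the relationship between EUS and other imaging findings". Accuracy measures appear under Aim 2 and concern elastography: "Sensitivity and specificity and 95% confidence intervals will be calculated for diagnosis of CP by SWE using INSPIRE criteria", and also prediction of fibrosis on histology.

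Table 1 (Procedures and Imaging) lists "Rosemont and Conventional Criteria" for EUS, several separate findings for MRI and for CT, and the Cambridge criteria for MRI and ERCP. It gives no rule for calling a child positive on any modality.

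**The concern.** Benchmarking a test for diagnosis asks how well it separates children with CP from children without it. Sensitivity answers half of that question, and any test can raise its sensitivity by lowering its threshold. To claim that EUS is the better test, one must also know what happens in children without CP, for EUS and for each comparator.

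The plan supplies neither half for Aim 1.2. The hypothesis concerns sensitivity, but the planned tests address association and estimate no sensitivity. Specificity is not mentioned for grayscale EUS, MRCP, CT or ERCP. The investigators do have the measure in view elsewhere: the Aim 2.1 hypothesis is that "EUS and TUS elastography will have high specificity for CP".

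This matters because the Study Design section says the results may feed into pediatric EUS criteria for CP and early CP. Aim 1 itself says it is unknown whether the existing adult criteria apply to children. Over-calling in children is therefore one of the things this pilot most needs to measure.

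**Working it through.** **The plan's own figures.** Study Procedures gives 40 children with ARP or CP and 20 controls: 40 + 20 = 60, which matches the stated enrolment of about 60. The ARP/CP split, the number of children with a comparator scan, and all accuracy rates are not given. No accuracy or power figure exists to reproduce, so every rate below is an assumption used for illustration.

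**What is planned for each test as a diagnosis of CP**

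| Test | Sensitivity | Specificity | Other planned analysis |
|---|---|---|---|
| SWE (EUS and TUS) | yes, 95% CI | yes, 95% CI | means, agreement |
| Grayscale EUS | hypothesis only | none | frequencies by group; association with other imaging |
| MRCP, CT, ERCP | hypothesis only | none | association with EUS |

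**Illustration 1: equal discrimination, different thresholds.** Assume both tests follow the same equal-variance binormal ROC curve with separation d. Then AUC = Φ(d/√2), and specificity = Φ(d − Φ⁻¹(sensitivity)). Take sensitivities of 85% and 70%: Φ⁻¹(0.85) = 1.036 and Φ⁻¹(0.70) = 0.524.

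| d | AUC | Specificity at 85% sensitivity | Specificity at 70% sensitivity | Loss (points, unrounded inputs) |
|---|---|---|---|---|
| 1.2 | 0.80 | Φ(0.164) = 56.5% | Φ(0.676) = 75.0% | 18.5 |
| 1.5 | 0.86 | Φ(0.464) = 67.9% | Φ(0.976) = 83.5% | 15.7 |
| 2.0 | 0.92 | Φ(0.964) = 83.2% | Φ(1.476) = 93.0% | 9.8 |

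An apparent 15-point gain in sensitivity is thus paid for by roughly 19 to 10 points of specificity, with no difference in discrimination.

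**Illustration 2: a limiting case.** Assume an EUS rule with no diagnostic value, positive in 70% of children whether or not they have CP. Compare it with a scan of sensitivity 50% and specificity 90%, with results independent within CP patients. The chance that the EUS rule shows the higher observed sensitivity is Σᵢ P(X = i)·P(Y ≤ i − 1), with X ~ Bin(n, 0.70) and Y ~ Bin(n, 0.50). This gives 0.76, 0.88 and 0.93 for n = 10, 20 and 30 CP patients. Varying the EUS positive rate from 60% to 80% gives a range of 0.59 to 0.99.

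**Precision if specificity is added.** When all n results are negative, the lower Clopper-Pearson 95% limit is 0.025^(1/n).

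- 20/20 negative: 83.2% to 100%
- 10/10 negative: 69.2% to 100%
- 5/5 negative: 47.8% to 100%
- 18/20 negative (full Clopper-Pearson): 68.3% to 98.8%

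The 20 is the planned control cohort. The 10 and 5 are assumed numbers of controls who also have a given comparator scan.

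**The case against.** The strongest reply is that this is a pilot with no power calculation and no decision rule, and that part of the gap is already covered. Aim 1.1 reports EUS findings in all 20 controls, which is the raw material for an EUS false-positive rate. The Study Design section also says grayscale EUS will be benchmarked against histology in surgical patients. Both points stand in part. But Aim 1.1 gives no corresponding rate for MRCP, CT or ERCP, so it cannot show whether extra sensitivity was bought with specificity. The histology comparison is confined to surgical patients, and the statistics section gives no analysis of grayscale EUS against it. Blinded reading of MRCP and CT limits reader bias but does not correct a threshold difference.

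Three stronger readings are tempting, and the documents do not support them.

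- A reader might infer that the plan will compare sensitivities and omit only specificity. In fact no sensitivity is planned for grayscale EUS or the comparators; it appears only in the hypothesis.
- A reader might infer that two EUS criteria sets mean a child counts as EUS-positive on either. No such rule is stated. The Background explains that adult criteria are used because no validated pediatric set exists. Undefined positivity also affects MRI and CT, so EUS is not shown to be the favoured test.
- A reader might infer from the illustrations that EUS will over-call here. They rest on assumed rates and show what could happen unseen, not what will.

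There is also a real difficulty with adding specificity against INSPIRE status as it stands. The Definitions section lets qualifying findings on MRI/MRCP, CT, ERCP or EUS establish CP. A child with such a finding becomes a CP case, so that finding can never count as a false positive. In ARP, an EUS-positive child who does not meet the definition may have true early CP, which is the stated target of the aim. Any added analysis has to deal with this.

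**Conclusion.** The point holds as a gap in analysis. Aim 1.2 claims a diagnostic benchmark, hypothesises sensitivity only, and has a planned analysis that estimates no accuracy measure for grayscale EUS or its comparators. A conclusion that EUS is more sensitive could reflect a lower threshold alone, and nothing planned would reveal it. Under the assumption of equal ROC curves, the specificity cost hidden behind an 85% against 70% sensitivity contrast is about 19 points at AUC 0.80 and 10 points at AUC 0.92. Those figures depend on the assumed AUCs, sensitivities and binormal form, none of which comes from the documents.

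No stated figure is wrong. For a pilot, the consequence is over-interpretation, carried into later work on pediatric criteria. The change is worth making because it is cheap and uses images the study already plans to review.

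**What to change.** Add under Aim 1 in the Statistical analysis section:

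> For each comparator, in children with both EUS and that scan within the ± 3 month window, sensitivity and specificity of each test will be reported with 95% CIs, together with paired differences and their 95% CIs (McNemar test). CP status for this comparison will be assigned without using the study EUS or the comparator scan being compared, relying on other qualifying imaging or on histology where available. Specificity will be shown separately in controls and in ARP without CP. Controls are the main specificity group; ARP results will be read with caution because EUS-positive ARP may be early CP. Rosemont and Conventional criteria will be reported separately and not combined as either-positive. Positivity will be fixed in advance for every modality. Aim 1.2 conclusions will be worded on sensitivity and specificity together.

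The cost is one paragraph of text, agreement on positivity rules before images are scored, and a CP classification for each comparison that leaves out the two tests concerned. No procedures or participants are added.

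There are two drawbacks. Comparator scans are done only when clinically indicated, so few controls may have one and specificity intervals will be wide (48% to 100% if only five controls are scanned and all are negative). Some children may also be unclassifiable once the two tests are set aside; their number should be reported. Where paired specificity cannot usefully be estimated, EUS specificity in all 20 controls is the fallback. It should be labelled as saying nothing about the comparators.

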**Definitions:**

Acute pancreatitis (AP): The presence of at least 2 out of 3 criteria: 1) abdominal pain (acute onset, epigastric, possibly radiating to the back); 2) serum amylase and/or lipase of at least 3 times greater than the upper limit of normal; and 3) characteristic findings of acute pancreatitis on imaging such as ultrasound, computed tomography, magnetic resonance imaging (i.e. pancreatic edema, areas of pancreatic or peripancreatic necrosis, peripancreatic inflammation).[18]

Acute Recurrent Pancreatitis (ARP): The presence of at least 2 distinct episodes of AP as defined above, along with 1) complete resolution of pain and a >1 month pain-free interval between diagnoses of AP; or 2) complete normalization of serum amylase and lipase before the subsequent episode of AP is diagnosed, along with complete resolution of pain, irrespective of a specific time interval.[18]

Chronic Pancreatitis (CP): The presence of at least one **irreversible structural change\*** in the pancreas with or without abdominal pain +/- exocrine pancreatic insufficiency +/- diabetes.[18]

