***\*irreversible structural changes:***

- *Ductal calculi, dilated side branches, parenchymal calcifications found in any imaging (abdominal ultrasound (abd US), magnetic resonance imaging/magnetic resonance cholangiopancreatography (MRI/MRCP), computerized tomography (CT), endoscopic retrograde cholangiopancreatography (ERCP), endoscopic US (EUS).*

- *Ductal obstruction or stricture/dilatation/irregularities that are persistent (for >2 months) on any imaging.*
- *Parenchymal atrophy, irregular contour, accentuated lobular architecture, cavities alone are not diagnostic findings for CP.*
- *Surgical or pancreatic biopsy specimen demonstrating histopathologic features compatible with CP (acinar atrophy, fibrosis, protein plugs, infiltration with lymphocytes, plasma cells, macrophages).*

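### Hypothesis 1.2 claims higher EUS sensitivity at every stage of CP, but the plan defines no stage and plans no sensitivity analysis for EUS or its comparators, so it cannot be tested as planned

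*Combined protocol and SAP*

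**What the plan says.** Under SPECIFIC AIMS, Aim 1.2 is headed "Benchmark grayscale EUS against other imaging modalities for diagnosis of CP, particularly early CP, in children", and its hypothesis is "Grayscale EUS findings will be more sensitive than other imaging modalities in all stages of CP". The comparators are ERCP, MRCP and CT, used only when done for clinical reasons within 3 months of the EUS.

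STUDY PROCEDURES describes the cases: "Forty participants will have ARP or CP as defined by the International Study Group of Pediatric Pancreatitis". Definitions makes CP a yes/no condition: at least one irreversible structural change "in the pancreas with or without abdominal pain +/- exocrine pancreatic insufficiency +/- diabetes". Changes that qualify include "Ductal calculi, dilated side branches, parenchymal calcifications found in any imaging", and the list of imaging that follows includes abdominal ultrasound, MRI/MRCP, CT, ERCP and EUS. A compatible surgical or biopsy specimen also qualifies.

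For Aim 1, Statistical analysis says "Frequencies will be used to describe the presence of EUS findings in patients with ARP, CP and controls". Groups are compared by Fisher's exact and chi-square tests. For EUS against other imaging it adds "These tests will also be used, as appropriate to compare the relationship between EUS and other imaging findings". Sensitivity appears only under Aim 2: "Sensitivity and specificity and 95% confidence intervals will be calculated for diagnosis of CP by SWE using INSPIRE criteria", and for predicting fibrosis on histology.

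Two graded tools appear under Procedures and Imaging: Cambridge criteria for MRI and ERCP, and a four-stage histologic fibrosis score. Neither is named as the stage variable for Aim 1.2. STUDY DESIGN also says that grayscale EUS will be benchmarked against histology in surgical patients, but Statistical analysis contains no matching analysis.

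**The concern.** A hypothesis of higher sensitivity at all stages needs three things: a stage for each CP case, a sensitivity for each modality within each stage, and a paired comparison of those sensitivities. The plan specifies none of them for grayscale EUS and its comparators.

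Any later statement that EUS is better in early CP would therefore rest on an analysis chosen after the data were seen. Two convenient choices would be weak. Sensitivity against INSPIRE CP is affected by the compared tests helping to define who has CP. Staging by Cambridge grade takes the stage from MRI or ERCP, which are themselves being compared with EUS. The study is meant to supply groundwork for pediatric criteria for CP and early CP, so an unsupported statement on early disease could carry forward into that work.

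**Working it through.** The documents give no power or precision figure to reproduce; they say that no power calculation was done because this is a pilot. The check has two parts.

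**1. Does any planned analysis answer the hypothesis?**

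| Needed | What the plan gives |
|---|---|
| CP stage per case | ARP, CP or control only; CP is yes/no; early CP undefined |
| Sensitivity of EUS, MRCP, CT, ERCP | None; sensitivity is planned for elastography only |
| Paired comparison | Association tests (Fisher's exact, chi-square) |
| Results by stage | None |
| Independent reference | Imaging findings, including those of EUS, MRCP, CT and ERCP, can establish CP |

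The association tests do not fill the gap. Among n CP cases imaged by EUS and one comparator, let a be positive on both, b on EUS only, c on the comparator only, and d on neither. Then:

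- EUS sensitivity = (a + b)/n; comparator sensitivity = (a + c)/n.
- Their difference = (b − c)/n, which depends only on the discordant cases.
- Fisher's exact or chi-square asks whether ad/(bc) differs from 1, that is, whether the two results are related. Two modalities can be strongly related with equal or with unequal sensitivities.

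**2. What could the sample show if stages were added?**

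Inputs from the documents: 40 pancreatitis participants, 20 of them undergoing resection, and four fibrosis stages. Assumptions: an even spread over stages, observed sensitivity near 80%, and every case having CP and the comparator scan. The last is optimistic, because ARP cases and missing scans reduce n.

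Exact (Clopper-Pearson) 95% limits for x of n are: lower = the 0.025 quantile of Beta(x, n − x + 1); upper = the 0.975 quantile of Beta(x + 1, n − x).

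Power is for a two-sided exact McNemar test at 0.05. The assumed gain is 30 points: 35% positive on EUS only and 5% on the comparator only.

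| Group | n | x/n | Exact 95% CI | Power |
|---|---|---|---|---|
| All cases | 40 | 32/40 | 64.4% to 90.9% | 86% |
| Half of the cases | 20 | 16/20 | 56.3% to 94.3% | 46% |
| 40 over 3 stages | 13 | 10/13 | 46.2% to 95.0% | 18% |
| 40 over 4 stages | 10 | 8/10 | 44.4% to 97.5% | 7% |
| 20 resected over 4 stages | 5 | 4/5 | 28.4% to 99.5% | 0% |

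For assumed gains of 20 to 40 points, with 5% positive on the comparator only throughout, power runs from 57% to 97% at n = 40, 5% to 38% at n = 13, and 2% to 19% at n = 10.

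The zero at n = 5 is structural. With m discordant pairs all in one direction, two-sided p = 2 × 0.5^m. That is 0.0625 for m = 5 and 0.031 for m = 6, so a stage with fewer than 6 patients cannot reach 0.05.

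**The case against.** The strongest defence is that this is a pilot. The experiment under Aim 1.2 promises only to test associations and correlate findings, and STUDY DESIGN offers the data as preliminary. That limits the consequence and explains the missing power calculation. It does not explain a directional hypothesis with no matching variable or analysis.

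A second defence is that the gap is simply a missing definition, and that defining early CP would also meet the concern. For the stage wording this is largely right. It would still leave overall sensitivity unplanned and the reference standard overlapping with the tests.

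Several stronger readings are tempting, and the documents do not support them:

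- **Early disease can never count as CP.** Dilated side branches seen on EUS qualify, and so does compatible histology, with 20 resections planned. Because early CP is undefined, one cannot say that the definition leaves it out.
- **Cambridge staging guarantees that EUS wins.** A low grade on one modality handicaps that modality, not the others, and EUS may be negative too. What the grades contain is in a cited source, not in these documents. The supportable point is that such a grade is not an independent stage measure.
- **Histology is the only non-imaging measure of severity.** The data that may be collected include pancreatic function tests, laboratory values and clinical course. Histology is, however, a graded score already in the plan and independent of imaging.

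**Conclusion.** The point stands in this form: hypothesis 1.2 cannot be tested as planned. A reader might infer that it cannot be tested at all, but that goes too far, since graded data will be collected and a stage variable could be prespecified. A reader might also infer that the plan at least compares modalities in CP overall. It does not, because no sensitivity of grayscale EUS or its comparators is planned even overall.

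These gaps are read directly from the documents and need no assumption. The figures for size do rest on assumptions about spread over stages, sensitivity near 80% and discordance. Under those assumptions, an overall comparison could be informative at best (86% power for a 30-point gain if all 40 cases had CP and the comparator scan), while results by stage can only be descriptive. The overlap between the CP definition and the compared tests is certain in principle. Its size cannot be given, because the documents do not say which modality established CP in each child.

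**What to change.** - **SPECIFIC AIMS, Aim 1.2:** limit the hypothesis to sensitivity for CP overall, and label any statement on early CP or stage as exploratory. The interest in early disease can stay on that footing.
- **Statistical analysis, Aim 1, paired estimates:** for EUS and each of MRCP, CT and ERCP, report paired sensitivities with exact 95% intervals in CP participants who had both tests. State what counts as positive on each modality. Acknowledge that the same modalities can contribute to the CP diagnosis.
- **Statistical analysis, Aim 1, histology table:** add a descriptive table of EUS and comparator positivity by the four-stage fibrosis score in the roughly 20 resected participants. This carries out the EUS benchmarking already promised in STUDY DESIGN and adds the comparators.
- **Statistical analysis, staging rule:** state that a grade taken from a compared modality will not be used to stage cases.

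The cost is wording in two sections, one set of paired estimates and one table, all from data already to be collected. The sponsor gives up the all-stages claim and accepts wide intervals within stages. Relabelling does not remove the overlap with the CP definition; the histology table offers a graded reference independent of imaging, in the resected participants only.
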